There is therefore an urgent need to more clearly understand: (a) the prevalence of the infection in the wider community in Northern Ireland (b) genetic and comorbidity factors predisposing individuals to more severe infection and higher risk of death (c) immune and inflammatory response during active infection and recovery.

With a clearer understanding of these SARS-CoV-2 characteristics at both population and biology levels we will be better equipped to cater our ongoing regional response. This study could help inform the regional strategy of exit from lock-down, identify at risk individuals with specific predisposing factors at a global level and advance our knowledge of the underlying genetics and immune biology which dictate response to infection. It is hoped that understanding the pathology of SARS-CoV-2 could help to reduce the mortality rate amongst individuals who are particularly vulnerable to this infection. This research is a collaboration between Ulster University and Queens University and will take place across three trusts areas in N. Ireland namely Western Health and Social Care Trust (WHSCT) to include The South West Acute Hospital, Fermanagh, Southern Health and Social Care Trust (SHSCT) and Belfast Health and Social Care Trust (BHSCT).

Overall Purpose/objectives

The overall purpose of the COVRES study is to provide preliminary data on prevalence and factors influencing severity of the infection in the NI population.

The core objectives are:

- a. To measure IgG to SARS-CoV-2 in a representative sample of the NI population at community level (nursing home), in hospitalised and non-hospitalised SARS-CoV-2 positive cases and in frontline healthcare staff.
- b. To perform whole genome sequencing on phlebotomy blood samples from hospitalised SARS-CoV-2 positive cases and frontline healthcare staff and collect associated SARS-CoV-2 PCR test data, comorbidity and medication data.
- c. To analyse immune cell and inflammatory responses in hospitalised and non-hospitalised SARS-CoV-2 positive cases and frontline healthcare staff.
- d. explore the relationship between host genotype, viral genotype, phenotypic and other data with (i) predisposition to Covid19 infection, (ii) severity (iii) treatment response if appropriate: drug/Vaccine/intervention and (iv) disease epidemiology.

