Study Design: This study will undertake: (a) the collection of retrospective waste plasma/serum samples from Covid-19 positive patients and extract from existing nasopharyngeal swabs and (b) the recruitment of Covid-19 positive hospitalised and non-

hospitalised and nursing home patients, hospital and nursing home staff, for whole genome sequencing, human host genomic analyses and viral genomic analyses. This research study will take place across three trust areas in Northern Ireland and will be conducted simultaneously in four phases, namely:

Phase 1- Rapid access of waste serum/plasma samples from hospital laboratories

Phase 2- Rapid access of nasopharyngeal swab extract, collected from patients, NHS and nursing home staff and members of the public.

Phase 3- Recruitment of SARS-CoV-2 patients who have tested positive by virus PCR assay from both hospitals and trust affiliated nursing homes and community.

Phase 4- Recruitment of hospital-tested and nursing home staff

Recruitment of participants and sample collection

Rapid Access to retrospective samples from hospital laboratories:

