For the remaining core objectives, a predictive model would be built and tested for the severity of COVID-19 in infected individuals. Multi-predictor variable regression modelling would be the appropriate technique to achieve these. Disease severity will be the primary dependent variable of interest, with age, comorbidity, gender, immune response measure, viral strain, and host genetics as candidate predictor variables, although some of them may turn out to be non-significant predictors. Therefore, we anticipate 5-predictor models to be constructed from the dataset. Based on the Guideline of TRIPOD on the EPV (events per predictor variable), we used the following to determine the appropriate samples size i.e. 4 levels of severity measure X 20 events per predictor X 5 predictors = 400. Allowing for some loss of sample due to follow up we estimate that recruiting a sample of $n=500$ total infected individuals from both settings is sufficient for our study. The 20 EPV is considered to be a small to medium dataset and it is well above the minimum 10 EPV recommended for building predictive models.

Standard approaches will be used to detect patterns in missing data. Data will be modelled using bespoke packages (such as DADA2 for 16S rRNA, or RnBeads for epigenetics) in R, or using approaches in Galaxy, tools from Bioconductor or similar. Data exploration approaches such as PCA and hierarchical clustering will be used to look for trends and possible confounders in the data. Post-treatment outcome data will be summarised both in graphical and tabular form for each metric. Patients will be assigned non-response or good response status based on primary outcome measures. The data will be analysed to examine any relationships between host/viral genomic data, OLINK, CRP, flow cytometry immune cell data and outcome measures. Other established statistical hypothesis testing methods, including t-tests, ANOVA, linear models, or non-parametric tests depending on the distributions of the measures observed will be used to analyse secondary outcomes

References

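### The good-response/non-response label is applied to patients without condition in a study that assigns no treatment, so it would carry disease severity rather than response

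*Protocol*

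**What the plan says.** Two consecutive paragraphs of the protocol's Statistical Analysis section bear on this point.

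- **Severity model.** The first paragraph says "Disease severity will be the primary dependent variable of interest" and, on method, "Multi-predictor variable regression modelling would be the appropriate technique to achieve these". The sample size is "4 levels of severity measure X 20 events per predictor X 5 predictors = 400", raised to 500 infected individuals for loss.
- **Response status.** The second paragraph says "Post-treatment outcome data will be summarised both in graphical and tabular form for each metric" and then "Patients will be assigned non-response or good response status based on primary outcome measures". The next sentence relates host and viral genomic data, OLINK, CRP and flow cytometry to outcome measures, without saying which.

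Treatment response appears in one other place, the last core objective (d), as "iii) treatment response if appropriate: drug/Vaccine/intervention". The Study Design section describes sample collection and recruitment for sequencing, beginning "This study will undertake: (a) the collection of retrospective waste plasma/serum samples from Covid-19 positive patients". It allocates no treatment.

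**The concern.** A response status needs three things: a treatment, a state before it, and a later state to compare. The rule names none of them, and it carries no condition limiting it to treated patients. The only primary variable the protocol identifies is severity. If the status is derived from severity, a patient who was never treated and stayed mild falls into the good-response class, and a patient who arrived severely ill falls into the non-response class.

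Any genomic or immune marker associated with that label could then be reported as a marker of treatment response when it is a marker of how ill the patient was. This is confounding by severity built into the outcome definition, and a larger sample would not remove it.

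**Working it through.** **1. The plan's own figure.** 4 levels × 20 events per predictor × 5 predictors = 400, as stated. The rise to 500 equals 400 / (1 − 0.20). The 20% is my assumption, since that paragraph gives no rate. The severity model is therefore sized on four levels, and no two-class outcome enters the calculation.

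**2. The rule set against the design.**

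| What a response status needs | What the protocol provides |
|---|---|
| A treatment | None assigned (Study Design). Medications are recorded by questionnaire at each timepoint, with care records as back-up (Data Collection for all cohorts). |
| A time origin at treatment start | Patient samples run from symptom onset: 0–10 days, 14–28 days, then 3 to 18 months (Sample Collection, patient recruitment). |
| Patients who were treated | Eligible patients include asymptomatic, non-hospitalised and suspected cases (Inclusion criteria). |
| An outcome that measures change | Disease severity, a state (Statistical Analysis). |
| A scope that matches the objective | Objective d(iii) is conditional; the assignment rule is not. |

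The last row is a direct disagreement between two parts of the protocol. The other rows show why the condition in the objective is needed: without it, the label has no reference point in an unknown share of patients.

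**3. What a two-class split would cost if it replaced the severity scale.** This step is conditional. Under proportional odds and small effects, the information in an ordinal outcome with level proportions p is proportional to 1 − Σp³. For a binary cut at q it is 3q(1 − q). Relative efficiency is the second divided by the first. The protocol gives no severity distribution and no cut, so both are assumed here.

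*Four equal levels:* 1 − 4 × 0.25³ = 0.9375.
- Middle cut: 3 × 0.5 × 0.5 = 0.75; 0.75 / 0.9375 = 0.80; 400 patients act as 320.
- Outer cut: 3 × 0.25 × 0.75 = 0.5625; 0.5625 / 0.9375 = 0.60; 400 act as 240.

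*Levels of 50/30/15/5%:* 1 − (0.125 + 0.027 + 0.003375 + 0.000125) = 0.8445.
- Cut after the first level: 0.75 / 0.8445 = 0.89.
- Cut after the second: 0.48 / 0.8445 = 0.57.
- Cut after the third: 0.1425 / 0.8445 = 0.17.

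*Levels of 70/15/10/5%:* 0.97, 0.59 and 0.22 by cut.

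**4. Events per predictor under the same condition.** With 400 patients and 5 predictors, equal levels give 200 / 5 = 40 in the smaller class at the middle cut and 100 / 5 = 20 at an outer cut. With 5% in the top level, a cut there gives 20 / 5 = 4, below both the planned 20 and the minimum of 10 that the protocol quotes.

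**The case against.** The strongest reply is that the status simply serves objective d(iii). The preceding sentence concerns post-treatment data, treatment response is a listed exploratory aim, and medication data and drug metabolites are collected. Lack of assignment bars causal attribution but does not bar a descriptive response status in treated patients. The definition, cut and analysis set are commonly left to a SAP, which is not shown here. Most of this stands as an account of what was probably intended, and the missing cut is not itself a finding. It does not repair the text: the rule as stated is unconditional where the objective is conditional.

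A reader might infer more than the protocol supports, in four ways.

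- **That the plan discards the four-level outcome.** It does not say so. Severity remains the dependent variable of the regression, and the response sentence reads as an additional analysis. The protocol also never calls the scale ordinal.
- **That the omics associations lose power.** They are related to outcome measures, not to the response status. The text leaves open which outcome is meant, but it does not choose the two-class one.
- **That staff are labelled too.** The sentence concerns patients, and staff are a separate cohort.
- **That no pre-treatment measure exists.** The recruitment sample falls within 10 days of symptom onset. It is not guaranteed to precede treatment, but it is not excluded for every patient.

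**Conclusion.** The point holds as a fault in a stated rule. The protocol assigns response status to patients without condition, in a study with no assigned treatment and no treatment-based time origin. This conflicts with the conditional wording of objective d(iii). Followed literally, the label would carry severity rather than response.

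The size of that distortion cannot be fixed from the document, because the proportion treated, the outcome measures meant and the cut are all unstated. The efficiency figures (0.80 or 0.60 for equal levels; 0.17 to 0.97 across the distributions shown) are arithmetically sound. They rest on proportional odds, on assumed distributions and on a replacement of the severity scale that the protocol does not state. They illustrate what that choice would cost and are not a measured defect of this plan.

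**What to change.** Amend the second of the two paragraphs in the Statistical Analysis section as follows.

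1. Confine the response status, and the post-treatment wording, to objective d(iii). Apply it only to patients with a recorded treatment and a measure taken before that treatment started.
2. Adjust that analysis for severity at treatment start, and describe its results as non-causal.
3. State that the genomic, OLINK, CRP and flow cytometry associations use the four-level severity outcome, not the two-class status.

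The cost is protocol wording and a smaller set for the response analysis. Medication and clinical data are already to be collected. The protocol does not say whether treatment start dates are recorded, so these may have to be taken from the care records that participants have consented to open.
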